#### 6.9.2. Criteria for Individual Dose Modification

Dose modification and discontinuation criteria for participants with ALT elevations or flare by treatment and cohort are provided in Section 7.7 Toxicity Management

## 6.9.3. Study and/or Cohort Discontinuation Criteria

Study treatment(s) that is considered related by the investigator(s) to the graded toxicities in a cohort will be held in all participants if  $\geq 3$  participants experience a Grade 3 AE or  $\geq 2$  participants experience a Grade 4 or SAE (excluding ALT), in the same system organ class (SOC). Decisions to reinitiate continuation of dosing will be made by the medical monitor upon review of all safety data generated by participants dosed to date.

Study and/or cohort may be discontinued at the request of Gilead, a regulatory agency, or an IRB or IEC.

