### Selgantolimod + Nivolumab

In the Phase 1b study, GS-US-493-5342, the combination of SLGN 3 mg oral once weekly plus nivolumab 0.3 mg/kg IV every 4 weeks for 12 weeks was evaluated in 14 participants with CHB. The combination treatment for 12 weeks was generally safe and well tolerated. The most common (> 1 participant) AEs considered related to study drugs by the investigator were nausea (n = 6), vomiting (n = 5), headache (n = 2), diarrhea (n = 2), and fatigue (n = 2). To mitigate the risk of nausea and vomiting, the use of antiemetics (eg, ondansetron) was allowed during the study. No Grade 3 or 4 AEs or SAEs were reported, and no Grade 3 laboratory abnormalities were observed. A single Grade 4 laboratory abnormality of elevated lipase was reported in 1 asymptomatic participant at posttreatment Week 4 that resolved to below upper limit of normal (ULN) 12 weeks later.

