## 6.9. Assessments for Early Discontinuation of Study Treatment

## 6.9.1. Criteria for Discontinuation of Study Treatment

Study treatment(s) that are considered related by the investigator to any of the below event(s) will be held in a participant until resolution of the event:

- Any study drug-related AE  $\geq$  Grade 3
- A confirmed, clinically significant laboratory test abnormality (other than ALT) ≥ Grade 3 considered study drug(s) related by the investigator

Study treatment(s) may be reinitiated following resolution of the above event(s) after discussion with the medical monitor. Study treatment(s) should be restarted in line with their preassigned schedules.

Study treatment(s) that are considered related by the investigator to any of the below events will be permanently discontinued:

- Any on-treatment uveitis, confirmed by ophthalmologic evaluation
- Any confirmed recurrence of study drug—related Grade 3 or 4 (excluding laboratory abnormalities) AE following dose interruption mandates permanent discontinuation of study drug(s)
- Unacceptable toxicity or toxicity that, in the judgment of the investigator, compromises the ability to continue study-specific procedures or is considered not to be in the participant's best interest
- Any study drug-related Grade 4 AE (excluding laboratory abnormalities)
- Any study drug—related ≥ Grade 3 AE not able to be medically managed (eg, nausea with antiemetics)
- Any confirmed study drug-related laboratory abnormality  $\geq$  Grade 3 following rechallenge
- A clinically significant Grade 4 laboratory abnormality
- Virological breakthrough: as defined in Section 2

Additional criteria for permanent discontinuation of study treatment(s):

- Intercurrent illness that would, in the judgment of the investigator, affect assessments of clinical status to a significant degree
- Hepatic disease progression or lack of efficacy defined as participants in Cohorts 1 and 2 (Group A) who do not achieve HBsAg decline ≥ 0.2 log10 IU/mL at Week 12
- Participant requests to discontinue for any reason
- Participant noncompliance
- Pregnancy during the study
- At the discretion of the investigator, Gilead, a regulatory agency or an institutional review board (IRB), or independent ethics committee (IEC).

If a participant discontinues study dosing (eg, as a result of an AE), every attempt should be made to keep the participant in the study and continue to perform the required study-related FU and procedures.

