## 7.2.2. Assessment of Severity

The severity of AEs will be graded using the Gilead Sciences Inc. (GSI) Toxicity Grading Scale, Version 01 April 2015, with the exception of IRRs. For each episode, the highest grade attained should be reported as defined in the Toxicity Grading Scale (Appendix 11.5).

Grading of IRRs will be done according to the Common Terminology Criteria for Adverse Events (CTCAE) Version 5.0 found on the National Cancer Institute (NCI) website:

 $https://ctep.cancer.gov/protocoldevelopment/electronic\_applications/docs/CTCAE\_v5\_Quick\_R\\ eference\_5x7.pdf$ 

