## 7.7.3. Grade 4 Laboratory Abnormality or Clinical Event

- For a Grade 4 clinical event or clinically significant Grade 4 laboratory abnormality confirmed by repeat testing within 3 calendar days, the study drug should be permanently discontinued, and the participant managed according to local practice. The participant should be followed as clinically indicated until the laboratory abnormality returns to Day 1 of treatment or is otherwise explained, whichever occurs first. A clinically significant Grade 4 laboratory abnormality that is not confirmed by repeat testing should be managed according to the algorithm for the new toxicity grade.
- A Grade 4 laboratory abnormality or clinical event that is not considered clinically significant by the investigator may also be tested for confirmation and study drug continued at the discretion of the investigator.
- The study drug may be continued without dose interruption for a clinically nonsignificant Grade 4 laboratory abnormality (eg, Grade 4 CK after strenuous exercise or triglyceride elevation that is nonfasting or that can be medically managed).

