#### **8.6.2.** Adverse Events

Clinical and laboratory AEs will be coded using the MedDRA. System organ class, high-level group term (HLGT), high-level term (HLT), preferred term (PT), and lower-level term (LLT) will be attached to the clinical database.

Events will be summarized on the basis of the date of onset for the event. A treatment-emergent AE (TEAE) will be defined as:

- Any AE that begins on or after the date of first dose of any study drug and no later than 30 days posttreatment of SLGN + nivolumab ± VIR-2218
- Any AE leading to premature discontinuation of any study drug

Summaries (number and percentage of participants) of TEAEs (by SOC and PT) will be provided by treatment group:

- All TEAEs
- TEAEs of Grade 3 or higher
- All TE treatment-related AEs
- TE treatment-related AEs of Grade 3 or higher
- All TE SAEs
- All TE treatment-related SAEs
- All TEAEs leading to premature discontinuation of any study drug
- All TEAEs leading to temporary interruption of any study drug
- AEs of special interest (eg, uveitis)

Summaries (number and percentage of participants) of all on-treatment and posttreatment potential irAEs (by SOC and PT), as defined by relevant MedDRA Standardised MedDRA Queries (SMQs), will be provided by treatment group.

All AEs collected during the study will be presented in the data listings.

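### Read as written, the cohort hold in Section 6.9.3 is not triggered by two non-serious Grade 3 AEs plus one Grade 4 AE in one SOC, although three Grade 3 AEs trigger it

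*Supplement*

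**What the plan says.** Section 6.9.3 has two limbs, both counted within one SOC and both tied to toxicities that the investigator considers related.

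- First limb: at least three "participants experience a Grade 3 AE".
- Second limb: at least two "participants experience a Grade 4 or SAE (excluding ALT), in the same system organ class (SOC".

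If either limb is met, the treatment concerned is held in all participants, and the medical monitor decides on restarting after a safety review. The sponsor, a regulator or an IRB/IEC may also discontinue a cohort.

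Elsewhere the protocol marks the inclusive meaning when it wants it. Section 6.9.1 speaks of a "≥ Grade 3 AE not able to be medically managed", and Section 8.6.2 tabulates "TEAEs of Grade 3 or higher". On grading, Section 7.2.2 says: "For each episode, the highest grade attained should be reported as defined in the Toxicity Grading Scale (Appendix 11.5".

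For individual participants, Section 6.9.1 separates Grade 4 AEs from "A clinically significant Grade 4 laboratory abnormality". Section 7.7.3 names both kinds as well: "For a Grade 4 clinical event or clinically significant Grade 4 laboratory abnormality confirmed by repeat testing within 3 calendar days".

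**The concern.** A safety rule should not become more lenient when one of the events gets worse. In the first limb, Grade 3 stands without *or higher*, and an episode that reaches Grade 4 is reported as Grade 4. On the plain wording, that participant counts only in the second limb, where one is not enough.

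This is the protocol's only count-based hold for a whole cohort. Section 1.5 describes the risk of the three-drug combination as unknown. After nivolumab was stopped, VIR-2218 and SLGN continue to Week 36 in Cohort 1 and Cohort 2 Group A (Section 3.2.1), so the rule still applies. What could be lost is the automatic pause for the other participants until a fourth case appears.

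**Working it through.** The protocol gives no operating characteristics for the hold, so there is no figure to reproduce. The check is an enumeration, followed by probabilities under assumed rates.

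**Definitions.** Within one SOC, leaving ALT aside, count participants with related events, each in one class only:

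- *a*: a non-serious Grade 3 AE
- *b*: a Grade 4 AE, with no separate Grade 3 AE
- *c*: a serious Grade 3 AE

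**Rules.**

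- As written: hold if a + c ≥ 3 or b + c ≥ 2.
- First limb read as Grade 3 or higher: hold if a + b + c ≥ 3 or b + c ≥ 2.

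| a | b | c | First limb as written | Second limb | As written | Grade 3 or higher |
|---|---|---|---|---|---|---|
| 3 | 0 | 0 | 3 | 0 | hold | hold |
| 2 | 1 | 0 | 2 | 1 | **no hold** | **hold** |
| 1 | 2 | 0 | 1 | 2 | hold | hold |
| 0 | 3 | 0 | 0 | 3 | hold | hold |
| 1 | 1 | 1 | 2 | 2 | hold | hold |
| 3 | 1 | 0 | 3 | 1 | hold | hold |
| 2 | 2 | 0 | 2 | 2 | hold | hold |

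**Only one pattern differs.** For the readings to disagree we need a + b + c ≥ 3, a + c ≤ 2 and b + c ≤ 1. The first two give b ≥ 1. With the third, b = 1 and c = 0, so a = 2.

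**Size within a cluster.** Suppose three participants have such AEs, independently, none of the Grade 3 AEs is serious, and a share g of the AEs is Grade 4. Then P(2+1) = 3g(1 − g)².

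- g = 0.10: 3 × 0.10 × 0.81 = 0.243
- g = 0.20: 3 × 0.20 × 0.64 = 0.384
- g = 1/3: 3 × 1/3 × 4/9 = 0.444 (the maximum)
- g = 0.50: 3 × 0.50 × 0.25 = 0.375

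**Size in a group of 40** (the planned size of Cohort 1 and of Cohort 2 Group A). With assumed per-SOC rates p3 and p4, the probability of ending in exactly 2+1 is

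40!/(2! 1! 37!) × p3² × p4 × (1 − p3 − p4)³⁷, where the multiplier is 40 × 39 × 38 / 2 = 29,640.

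| p3 | p4 | P(exactly 2+1) |
|---|---|---|
| 1% | 0.5% | 0.8% |
| 2% | 1% | 3.8% |
| 5% | 1% | 7.5% |
| 5% | 2% | 10.1% |
| 5% | 5% | 7.5% |
| 10% | 2% | 5.2% |
| 10% | 5% | 3.6% |

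At 5% and 2%, the probability that the hold fires rises from 45.6% as written to 55.7% with the inclusive first limb. These figures cover cohorts that end at 2+1. A cohort that passes through 2+1 and goes on gets its hold one participant late.

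**The case against.** **A sensible medical monitor would count a Grade 4 event towards a Grade 3 threshold.** Section 7.2.2 says how to report a grade, not how to count for the hold, and nothing says that a Grade 4 participant drops out of the Grade 3 count. That is fair, and it makes this a fault of wording that judgement may repair. But the protocol writes the inclusive form where it wants it, and a stopping rule used at about 30 centers should not depend on inference.

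**A reader might infer that any two Grade 3 AEs plus one Grade 4 AE escape the hold.** The text does not support that. A serious Grade 3 AE counts in the second limb, so the hold fires if it is in a participant other than the one with the Grade 4 event. The first limb also fires if the Grade 4 participant had a separate Grade 3 AE in that SOC. Serious Grade 3 events are foreseeable: Appendix 11.5 defines Grade 3 pancreatitis partly by an indication for hospitalization.

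**A reader might infer that Grade 4 laboratory abnormalities fall outside the hold, because Grade 4 stands without a noun.** That is largely answered. The SOC condition points to coded AEs, and Section 8.6.2 codes laboratory AEs too. Section 7.6 requires an abnormality that leads to discontinuation to be recorded as an AE. What stays open is which grade counts, because Section 7.6 lets the AE grade differ from the laboratory grade. In the earlier SLGN plus nivolumab study of 14 participants, Section 1.5 says: "No Grade 3 or 4 AEs or SAEs were reported, and no Grade 3 laboratory abnormalities were observed. A single Grade 4 laboratory abnormality". That shows that the two counts can differ. It says nothing about how often the hold would fire: the lipase elevation came four weeks after treatment and its relatedness is not stated.

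**Other protection exists.** Related Grade 3 AEs are held and related Grade 4 AEs end treatment for the individual (Section 6.9.1). Potential irAEs of any grade go to the medical monitor (Section 7.7.4). The sponsor did stop nivolumab in all cohorts. All of this stands and limits the harm.

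**Conclusion.** The gap is real and one pattern wide: two participants with non-serious related Grade 3 AEs and a third, different participant with a related Grade 4 AE in the same SOC. There the literal rule gives no hold, although three Grade 3 AEs give one. It is worth correcting because the inversion is in a safety rule and costs almost nothing to remove.

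The 24% to 44% within three-participant clusters should not be taken as the chance that the hold fails in this trial. It assumes that a cluster already exists, and the Grade 4 share is invented. The 0.8% to 10.1% for a group of 40 also rests on assumed rates. The low end may be nearer to the single-agent experience: Section 1.5 reports one related Grade 3 AE and no related Grade 4 AE in the SLGN studies, with 102 participants with CHB in the two Phase 2 studies. Rates for the combination are unknown.

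The missing noun after Grade 4 is a minor clarification. With enrolment complete, nivolumab stopped and Group B off treatment, the benefit is confined to the remaining dosing in Cohort 1 and Cohort 2 Group A.

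**What to change.** Reword the trigger in Section 6.9.3 as: *≥ 3 participants experience an AE of Grade 3 or higher, or ≥ 2 participants experience a Grade 4 AE or SAE, in the same SOC (ALT elevations of any grade excluded from both counts)*.

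The ALT exclusion has to cover every grade. If only Grade 4 ALT were excluded, three Grade 3 ALT AEs could hold the cohort while three Grade 4 ALT events could not, and the same inversion would return. ALT has its own management in Section 7.7.5.

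If clinically significant Grade 4 laboratory abnormalities other than ALT are meant to count at their laboratory grade, add them by name, as Sections 6.9.1 and 7.7.3 do. No edits to Section 7.2.2 or Appendix 11.5 are needed.

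Cost: a few words and no new data. The hold can fire one participant earlier, in the 2+1 pattern only. If Grade 3 ALT AEs count in the first limb today, they no longer would.

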## Selgantolimod

Selgantolimod treatment alone have been evaluated in multiple Phase 1 and Phase 2 studies in both healthy volunteers and participants with CHB. The longest durations of treatment were evaluated in 2 Phase 2 studies, GS-US-389-2024 (NUC-suppressed participants with CHB) and GS-US-389-2025 (treatment-naive participants with CHB), that administered placebo, SLGN 1.5 mg, or 3 mg once weekly with a NUC for 24 weeks to 93 participants with CHB. Selgantolimod up to 3 mg once weekly was safe and well tolerated in 102 participants with CHB (48 participants in Study GS-US-389-2024 and 54 participants in Study GS-US-389-2025). Based on pooled safety review of the SLGN studies, 3 potential ADRs related to SLGN of nausea, vomiting, and iridocyclitis were identified. Majority of these ADRs reported have been mild or moderate in severity. To mitigate the impact of ADR of nausea and vomiting for SLGN, the use of antiemetic (eg., ondansetron) is allowed in the study. A Grade 2 iridocyclitis (in the SLGN 1.5-mg dose group) was the only SAE reported that was considered related to SLGN by the investigator and led to early study drug discontinuation. This occurred in a participant who tested positive for the human leukocyte antigen (HLA)-B27 haplotype, a genetic risk factor associated with various immune disorders including anterior uveitis. No Grade 3 or 4 AEs considered related to SLGN treatment have been reported in the studies, except for 1 Grade 3 AE of rhinorrhea considered possibly related by the investigator that was reported in Study GS-US-389-2025. Additional safety results can be found in the IB for SLGN.

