## 7.7. Toxicity Management

All clinical and clinically significant laboratory toxicities will be managed according to uniform guidelines detailed in Appendix 11.6.

- Grade 3 and 4 clinically significant laboratory abnormalities should be confirmed by repeat testing within 3 calendar days of receipt of results and before study drug discontinuation, unless such a delay is not consistent with good medical practice
- Clinical events and clinically significant laboratory abnormalities will be graded according to the Table for GSI Grading Scale for Severity of Adverse Events and Laboratory Abnormalities (Appendix 11.5)
- When restarting study drug following resolution of the AE, the study drug should be restarted at full dose or modified dose that is dependent upon discussion with the medical monitor
- Any recurrence of the study drug—related Grade 3 or 4 clinical or clinically significant laboratory AE following dose interruption mandates permanent discontinuation of study drug
- Administration of study drug(s) may be discontinued due to a clinical or laboratory event.
   The medical monitor should be consulted prior to dose discontinuation of study drug(s) unless the investigator believes that immediate action is warranted to ensure the continued safety of the participant
- Any questions regarding toxicity management should be directed to the medical monitor.

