## 7.7.2. Grade 3 Laboratory Abnormality or Clinical Event

- For Grade 3 laboratory abnormality or clinical event, study drug may be continued if the event is considered to be unrelated to study drug
- For any study drug-related, Grade 3 AE, study drug should be held
- For any study drug—related ≥ Grade 3 AE not able to be medically managed (eg, nausea with antiemetics), study drug should be permanently discontinued
- For a confirmed laboratory abnormality, study drug—related Grade 3, study drug would be held until toxicity returns to ≤ Grade 2. If a laboratory abnormality recurs to ≥ Grade 3 following rechallenge, study drug should be permanently discontinued, and the participant managed according to local practice. Recurrence of laboratory abnormalities considered unrelated to study drug may not require permanent discontinuation.

• For a Grade 3 clinical event, or clinically significant laboratory abnormality confirmed by repeat testing within 3 calendar days that is considered to be related to study drug, study drug should be withheld until the toxicity returns to ≤ Grade 2

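### Read literally, the cohort hold rule in 6.9.3 fires on three related Grade 3 participants but not on two Grade 3 plus one Grade 4 in the same organ class

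*Supplement*

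**What the plan says.** Section 6.9.3 (Study and/or Cohort Discontinuation Criteria) holds a treatment that the investigator considers related, in all participants, if either of two limbs is met. Limb 1 needs at least 3 "participants experience a Grade 3 AE or". Limb 2 needs at least 2 "participants experience a Grade 4 or SAE (excluding ALT), in the same system organ class (SOC"). The medical monitor decides on restarting after reviewing all safety data to date. The same section lets the sponsor, a regulator or an ethics board discontinue a cohort on request.

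Section 7.2.2 sets how an event is graded: "For each episode, the highest grade attained should be reported as defined in the Toxicity Grading Scale".

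Elsewhere the protocol uses inclusive wording when it means more than Grade 3. Section 7.7 speaks of recurrence of a "Grade 3 or 4 clinical or clinically significant laboratory AE following dose interruption mandates permanent discontinuation of study drug". Section 8.6.2 tabulates "TEAEs of Grade 3 or higher". Section 7.7.2 has two neighbouring bullets with different actions: for a related "Grade 3 AE, study drug should be held", and for a related "≥ Grade 3 AE not able to be medically managed (eg, nausea with antiemetics), study drug should be permanently discontinued".

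**The concern.** A safety trigger should never respond less to a worse pattern of events. Compare two cohorts, each with three participants who have related nonserious events in one organ class. If all three events are Grade 3, the drug is held for everyone. If one of them is Grade 4 instead, limb 1 has two participants and limb 2 has one, and nothing is held at cohort level.

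At stake is the automatic pause for participants who have not yet had an event, up to 37 in a cohort of 40. Section 6.9.3 is the only automatic group-level trigger that the protocol states. Section 1.5 calls the risk of the three-drug combination unknown. In the current version the rule matters for SLGN and VIR-2218 in Cohort 1 and Cohort 2 Group A, because nivolumab and all Group B treatment were stopped.

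**Working it through.** The protocol states thresholds but no trigger probability, so there is no figure of its own to reproduce. The check enumerates the rule and then sizes the gap under assumed rates. Counting is per cohort, as the text most naturally reads, and ALT events are left out.

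**Enumeration.** Let X3 be the participants with a nonserious Grade 3 event as their worst, S3 those with a serious Grade 3 event, and X4 those with a Grade 4 event, all related to the same drug and in the same organ class.
- As written: hold if X3 + S3 ≥ 3, or X4 + S3 ≥ 2.
- With limb 1 as Grade 3 or higher: hold if X3 + S3 + X4 ≥ 3, or X4 + S3 ≥ 2.

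| X3, S3, X4 | As written | Grade 3 or higher |
|---|---|---|
| 3, 0, 0 | hold | hold |
| 2, 0, 1 | **no hold** | hold |
| 1, 1, 1 | hold | hold |
| 1, 0, 2 | hold | hold |
| 2, 0, 0 | no hold | no hold |

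Over all combinations of 0 to 4 in each category, (2, 0, 1) is the only one on which the two versions differ. One serious event among the two Grade 3 events is enough to close the gap, because it counts in limb 2. From (2, 0, 1) the next participant always triggers: a third Grade 3 meets limb 1, and a second Grade 4 or an SAE meets limb 2. The delay is therefore one participant.

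**Size without an event rate.** Take exactly three affected participants, each with a nonserious Grade 3 or a Grade 4 event, and let q be the assumed Grade 4 share. The chance of no hold as written is 3q(1−q)²: 13.5% at q = 5%, 24.3% at 10%, 38.4% at 20%, a maximum of 44.4% at one third, and 37.5% at 50%. These figures are conditional on three such participants in one organ class, so they are not the chance that the gap occurs.

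**Size with assumed rates.** Let p3 and p4 be the chances per participant, for one drug and organ class, that the worst related event is nonserious Grade 3 or is Grade 4. Participants are independent and n = 40. The gap is

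40!/(2!·1!·37!) · p3² · p4 · (1−p3−p4)³⁷ = 29,640 · p3² · p4 · (1−p3−p4)³⁷.

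For p3 = 1% and p4 = 0.5% this is 29,640 × 0.0001 × 0.005 × 0.5717 = 0.85%.

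| p3 | p4 | Hold, as written | Hold, Grade 3 or higher | Gap (points) |
|---|---|---|---|---|
| 0.5% | 0.1% | 0.18% | 0.24% | 0.06 |
| 0.5% | 0.2% | 0.40% | 0.52% | 0.11 |
| 1% | 0.5% | 2.5% | 3.3% | 0.85 |
| 1% | 1% | 6.8% | 8.2% | 1.40 |
| 2% | 1% | 10.4% | 14.2% | 3.84 |
| 3% | 2% | 28.8% | 36.8% | 8.00 |

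**Which rows are plausible.** Section 1.5 (Selgantolimod) reports no related Grade 3 or 4 AE "except for 1 Grade 3 AE of rhinorrhea considered possibly related by the investigator", with 102 participants with CHB cited. That is 1/102 = 1.0% for Grade 3 (exact two-sided 95% upper limit 5.3%) and 0/102 for Grade 4 (3.6%), over all organ classes together. A rate for a single class should be lower, so the first two rows fit SLGN alone best. For VIR-2218 the same section describes related AEs of Grade 1 or 2 only, among 37 healthy participants and 24 with CHB. Higher rates for the combination are possible but are assumptions.

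**The case against.** **The wording may be meant as a floor.** A safety reader can take a Grade 3 AE to mean at least Grade 3. Section 7.2.2 governs how an episode is reported, not how 6.9.3 counts participants. The protocol is also not strict elsewhere: for the same individual hold, 6.9.1 writes Grade 3 or above and 7.7.2 writes Grade 3. This stands to the extent that the inclusive reading cannot be ruled out. It does not remove the point, because 6.9.3 does not say it, and the inclusive terms used elsewhere favour the literal reading.

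**Other safeguards act.** Section 6.9.1 holds or stops the drug in those affected, and restarting needs discussion with the medical monitor. SAEs reach the sponsor within 24 hours (7.4.1.1), and potential immune-related events are notified whatever their grade (7.7.4). The sponsor has already stopped nivolumab at its discretion. All of this softens the gap. It does not replace an automatic hold for the others.

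**Adding only the words or higher has a side effect.** The ALT exclusion sits in limb 2. Grade 4 ALT could then enter limb 1, although flares have their own algorithm in 7.7.5. This objection stands, and the fix has to deal with it.

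**Little dosing remains.** Enrollment was complete when nivolumab was stopped, and 40 is an upper bound on those still dosed. This also stands, and it limits the urgency.

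A reader might infer that an active hold is lifted when a participant's event worsens. The rule does not say that. Once three participants have reached Grade 3 the hold has fired. The comparison is between two patterns of events, not a sequence in one cohort.

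**Conclusion.** The point holds as a drafting gap: on its literal text the rule is not monotone in severity, in exactly one pattern. That pattern is two participants with related nonserious Grade 3 events plus one with a related non-ALT Grade 4 event, in the same cohort and organ class. The consequence is that the cohort hold comes one participant later.

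The size is small: roughly 0.8 to 8 percentage points per cohort of 40 at the higher assumed rates, and about 0.1 point or less at rates nearer the SLGN experience. These figures rest on independence between participants, on counting per cohort, and on event rates that the protocol does not give.

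Two stronger readings are not supported. One is that a Grade 4 event can under no reading count towards limb 1; the protocol's uneven grade wording leaves that open. The other is that participants are left unprotected; the individual rules and discretionary stopping remain in force. This is an optional improvement.

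**What to change.** Reword the trigger along these lines: *if, excluding ALT elevations in both counts, ≥ 3 participants experience an AE of Grade 3 or higher, or ≥ 2 participants experience a Grade 4 AE or an SAE, in the same SOC*. The thresholds, the organ-class condition and the medical monitor's review stay as they are. A worse grade then can no longer remove a hold, and ALT flares stay with the algorithm in 7.7.5. If the sponsor intends Grade 3 ALT to count in limb 1, it should say so and exclude only Grade 4 ALT there.

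The cost is one sentence and no new data. There would be a few more temporary holds, each leading to the review already specified. Outside ALT, the added holds arise only in the pattern of two Grade 3 and one Grade 4, with the frequencies in the gap column above. Section 9.2.1 requires ethics and regulatory approval for protocol modifications, so the change belongs in the next amendment or in the next protocol that reuses the rule. It does not justify an amendment of its own.
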